9.1.1.2. Bone marrow Specimens

9.1.1.2.1. Bone marrow aspirate specimens are collected at Screening and at end of Cycle 4 (16 weeks ± 7 days). In the event of a dry tap, the requirement for the bone marrow aspirate is waived (a biopsy is still required).

9.1.1.2.2. Bone marrow biopsy sections will be obtained at Screening and at end of Cycle 4. Sections will be obtained from hematopathology after clinical evaluation is complete. Unstained, sections will be cut from the residual tissue block. No separate research specimen is required.

9.1.2. Handling of Specimens(s):

9.1.2.1. Blood specimens are collected in standard EDTA (purple top) vacutainer tubes.

9.1.2.2. Bone marrow aspirate specimens will be collected into heparinized syringes and transferred to standard heparin (green top) vacutainer tubes.

9.1.2.3. Bone marrow biopsy sections will be obtained from Weill Cornell Medicine hematopathology director [name], PhD.

9.1.3. Shipping of Specimen(s): Specimens will be hand-delivered to the [name] Lab.

9.2. Molecular Response Reported by JAK2V617F, CALR type 1 or type 2, MPLW515L/K Driver Mutation Variant Allele Frequency

9.2.1. Collection of Specimen(s):

9.2.1.1. Blood specimens are collected at Screening, at end of Cycle 4 (16 weeks ± 7 days) and at End of Tier Test.

9.2.1.2. Bone marrow aspirate specimens are collected at Screening and at end of Cycle 4.

9.2.1.3. Bone marrow biopsy sections will be obtained from hematopathology after clinical evaluation is complete. Unstained, sections will be cut from the residual tissue block. No separate research specimen is required.

9.2.2. Handling of Specimens(s):

9.2.2.1. Blood specimens are collected in standard EDTA (purple top) vacutainer tubes.

9.2.2.2. Bone marrow aspirate specimens will be collected into heparinized syringes and transferred to standard heparin (green top) vacutainer tubes.

9.2.3. Shipping of Specimen(s): Specimens will be hand-delivered to [name] Lab.

10. Measurement of Effect

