12.4.2 Analysis of Secondary Endpoints

Clinical response to vactosertib will be assessed using the *Criteria for Clinical Benefit* outlined above as a composite endpoint. Patients achieving any of these criterial will be considered to have achieved clinical benefit. This endpoint will be used to define a preliminary estimate of the potential efficacy of vactosertib in the study population. Complete enrollment to both tiers (37 total) will allow us to confidently identify a *Clinical Benefit* response rate of more than 30%. This estimate has a significance of ≤ 0.1 and a power of 0.8 and is based upon a reported clinical improvement rate of $\leq 10\%$ (almost

entirely due to symptomatic response) in similar patient populations with best available therapy^{34,35}. Reported rates of splenic and/or erythropoietic responses to best available therapy are $\leq 3\%$. The 37 subjects enrolled on this study will allow Splenic Response and Erythropoietic Response rates of at least 20% to be individually tested with a power of 80% and a significance of $< 0.1\%$. If after complete accrual of 37 subjects, more than 11 patients meet criteria for Composite Response, or more than 7 patients meet criteria for Splenic or Erythropoietic Response, vactosertib will be considered to have sufficient efficacy for definitive testing in a randomized study.

The secondary endpoints of erythropoietic (HGB and RBC transfusion), symptomatic, and splenic responses will be directly tested as described in the preceding section. While limited by the small sample size, additional endpoints will be assessed including molecular (MPN driver variant allele frequency), pharmacodynamic (SMAD2/3 phosphorylation in bone marrow and/or blood CD34+ hematopoietic stem and progenitor cells), and histologic (bone marrow cellularity and fibrosis score) responses. The incidence of hematologic toxicities, infections, disease progression, thrombosis events, and the probability of overall and progression free survival, will be monitored. Secondary endpoints will be reported using descriptive statistics but no formal hypothesis testing will be performed.

Other secondary endpoints will be reported using descriptive statistics but no formal hypothesis testing will be performed. The following endpoints will be analyzed:

12.4.2.1 Histologic response defined by any reduction in grade of bone marrow fibrosis by histopathologic assessment at 16 weeks.

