12.4.2.2 Molecular response defined by a decrease in allelic ratio of MPN-driver mutations (eg. JAK2, CALR, and MPL allelic ratio) in blood and/or bone marrow cells.

12.4.2.3 Pharmacodynamic Response defined as any of the following:

- Reduced immunohistochemical staining for SMAD2/3 phosphorylation in bone marrow biopsy sections (See Figure 1).
- Reduced mean fluorescence intensity of SMAD2/3 phosphorylation staining in peripheral blood hematopoietic stem and progenitor cells (HSPCs) or mature progeny as assessed by flow cytometry (See Figure 2).
- Reduced mean fluorescence intensity of SMAD2/3 phosphorylation staining in bone marrow hematopoietic stem and progenitor cells (HSPCs) or mature progeny as assessed by flow cytometry.

12.4.2.4 ToxicityThe incidence of hematologic toxicities, infections, disease progression, thrombosis events, and the probability of overall and progression free survival, will be monitored.

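### Molecular and pharmacodynamic response count any decrease in any available specimen at no fixed visit, so the scored rate depends partly on how many samples a patient gives

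*Combined protocol and SAP*

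**What the plan says.** **Definitions.** Section 12.4.2.2 makes molecular response a "decrease in allelic ratio of MPN-driver mutations (eg. JAK2, CALR, and MPL allelic ratio) in blood and/or bone marrow cells". Section 12.4.2.3 opens with "Pharmacodynamic Response defined as any of the following" and lists three routes: biopsy staining, blood flow cytometry and marrow flow cytometry. Neither gives a visit, a lead specimen, a minimum size of decrease or a rule for missing samples. The endpoint list in the Protocol Summary and Section 10.4 add none. Histologic response, in the same list, does have a visit: "any reduction in grade of bone marrow fibrosis by histopathologic assessment at 16 weeks".

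**Molecular sampling.** Section 9.2.1.1 states: "Blood specimens are collected at Screening, at end of Cycle 4 (16 weeks ± 7 days) and at End of Tier Test". Tier 1 lasts four cycles (7.9.1), so its last two times coincide. End of Tier 2 testing follows Cycle 6 (6.3.6.6), so in Tier 2 they are weeks 16 and 24. There is one post-baseline aspirate in either tier (9.2.1.2). Section 9.1.1.2.1 adds: "In the event of a dry tap, the requirement for the bone marrow aspirate is waived", with the biopsy kept. Section 9.2.1.3 also lists biopsy sections under molecular response, without saying whether allele frequency will be measured on them.

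**Pharmacodynamic sampling.** Section 9.1.1.1 lists blood at screening, at End of Tier and one hour after dosing at each new dose level. Section 6.3.2.4 adds research blood on Day 1 of cycles and on C1D8, whether or not the dose changed. Section 6.2.2.9 describes the screening research specimens as serving both SMAD and allele-frequency work.

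**Cell population.** The opening text of 12.4.2 refers to "SMAD2/3 phosphorylation in bone marrow and/or blood CD34+ hematopoietic stem and progenitor cells". Section 12.4.2.3 also accepts mature progeny.

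**The concern.** When any decrease counts and no visit or specimen is fixed, each extra sample is another opportunity to be called a responder. The number of samples is not the same for everyone. It differs by tier, it may differ after a dry tap, and for pharmacodynamic blood it may follow the dose path. Part of any difference in reported rates, between tiers or between patients, would then reflect sampling.

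These two endpoints are the study's stated measures of on-target molecular activity (1.2.2). A rate that is high even when nothing has changed says little about that activity, and rates built from different numbers of looks should not be pooled or compared as they stand.

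**Working it through.** The plan states no expected rate, power or alpha for these endpoints, so there is no figure to reproduce. The calculation below illustrates what the rule does.

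**Assumptions (not from the documents).** No true change; symmetric measurement noise; any decrease counts; one baseline per specimen type.

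**Inputs from the documents.** Post-baseline blood times k = 1 (Tier 1) or 2 (Tier 2), from 9.2.1.1, 7.9.1 and 6.3.6.6. Post-baseline aspirates: 1, or 0 after a dry tap.

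**1. Molecular response, independent noise.** No blood sample falls below baseline only if the baseline is the smallest of k + 1 exchangeable values, which has probability 1/(k+1). Marrow shows no decrease with probability 1/2.

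- Without marrow: k/(k+1). Tier 1: 1/2 = 50%. Tier 2: 2/3 = 67%.
- With aspirate: 1 − [1/(k+1)] × 1/2. Tier 1: 1 − 1/4 = 75%. Tier 2: 1 − 1/6 = 83%.

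**2. Sensitivity to correlation.**

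| Assumption | Tier 1 with aspirate | Tier 2 with aspirate | Tier gap |
|---|---|---|---|
| Independent noise | 75% | 83% | 8 points |
| Blood-marrow noise correlation 0.5 | 67% | 77% | 10 points |
| Blood-marrow noise correlation 0.9 | 57% | 71% | about 13 points |
| All changes correlated 0.8 | 60% | 65% | 5 points |

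The 0.5 and 0.9 noise-correlation rows come from a simulation of 400,000 draws. The last row uses the equicorrelated values for two and three samples. Blood-marrow correlation shrinks the value of having marrow (Tier 1: 50% to 57% at 0.9, against 50% to 75% under independence). It does not remove the tier gap.

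**3. Pharmacodynamic response, blood alone, k/(k+1).**

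- List in 9.1.1.1: a patient kept at DL1 has C1D1 and End of Tier, k = 2, 67%. A patient escalated to DL4 with one restart has k = 6, 6/7 = 86%. The gap is 19 points.
- Adding the samples in 6.3.2.4: the patient kept at DL1 has C1D1, C1D8, Day 1 of Cycles 2 to 4 and End of Tier, k = 6, 86%. The escalated patient has about 9, 9/10 = 90%. The gap is about 4 points.

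**4. Pharmacodynamic composite, independent noise.** With biopsy staining and marrow flow added, the chance is 1 − 1/4 × 1/(k+1) with an aspirate and 1 − 1/2 × 1/(k+1) after a dry tap. At k = 2 this gives 92% and 83%; at k = 6, 96% and 93%. The no-change rate is high for everyone.

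**5. After fixing one specimen and one time.** Every patient has one comparison, so the no-change chance is equal across tiers and dry-tap status. It is still 50% while any decrease counts. A threshold with false-positive rate f brings it to f. For example, f = 10% gives 10% on one look, against 1 − 0.9² = 19% and 1 − 0.9³ = 27% on two and three independent looks.

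**The case against.** **Descriptive only.** Section 12.4.2 plans no formal test of these endpoints, and the Simon rule (12 then 37 patients, at least 1 then at least 4 responders) uses clinical benefit without dose-limiting toxicity. This stands: a reader who inferred a threat to the go/no-go decision would be wrong.

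**The dry-tap contrast.** A reader might infer that dry-tap patients have the lowest rate and are those with more fibrosis. The documents support neither firmly. Section 9.2.1.3 lists biopsy sections under molecular response, so a marrow route may survive a dry tap. No dry-tap frequency or link to fibrosis is given. The 50% and 67% figures therefore apply only if no marrow result is available.

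**The dose-path contrast.** Escalation requires an inadequate erythropoietic response (Table 3), so a reader might infer that hemoglobin non-responders get many more chances of a pharmacodynamic response, biasing its correlation with clinical outcome. With the 6.3.2.4 samples counted, the blood gap falls to about 4 points. Section 2.5.1 is background and describes a continuous intensity; Section 12 plans no correlation with responder status.

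**Day 1 samples used for allele frequency.** If they were, blood alone would give about 6 against 8 samples, 86% against 89%. The tier gap would narrow, but the no-change rate would be higher in both tiers.

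**Inference from silence.** No text says that any sample may be used. That follows from the absence of a visit. Since histologic response is given one, the omission matters.

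**Conclusion.** The point holds as a defect in the two definitions. Applied as written, they make the chance of being scored a responder rise with the number of samples. For molecular response on the 9.2 list, the no-change rate with an aspirate is 75% against 83% across tiers under independent noise. The tier gap is about 5 to 13 points over the correlation assumptions shown. The dry-tap gap is uncertain. For pharmacodynamic response, the difference between patients may be only a few points, and the larger problem is a no-change rate near the ceiling for all.

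The figures rest on an assumed noise model with no treatment effect. They do not support the stronger reading that the response rate reflects sampling and not the drug: a real effect would add to these rates. The consequence is limited to the interpretability of the reported rates and to pooling or comparing the tiers. It is worth correcting because the correction is cheap and these are the study's measures of target activity.

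**What to change.** - **Molecular response (12.4.2.2, with 10.4 and the Protocol Summary):** define it for every patient as blood allele frequency at screening versus end of Cycle 4, requiring a decrease larger than assay variability. The documents do not give that variability, so the laboratory should supply it and fix the threshold before results are reviewed. Fixing the specimen without a threshold would still leave a 50% no-change rate.
- **Pharmacodynamic response (12.4.2.3):** replace the any-of composite. Report biopsy staining, blood intensity and marrow intensity separately, each at one pre-specified paired time and in one named cell population. Keeping all three avoids a trade-off: the biopsy survives a dry tap but has no stated timing relative to dosing, whereas blood at a new dose level is drawn one hour after an observed dose.
- **Other specimens and weeks:** report separately, with the number of paired samples and of dry taps. State whether biopsy sections under 9.2.1.3 yield an allele frequency.
- **Sampling lists:** reconcile 9.1.1.1 with 6.3.2.4 and say which blood samples serve which endpoint.

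The cost is wording only, as the specimens are already scheduled. The downside is a lower headline molecular rate and no single pharmacodynamic responder rate.

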12.5 Interim Analysis

Reports of toxicity and efficacy will be submitted for DSMB review at the following time points:

- completion of Tier1;
- completion of Tier2;
- any time one of the stopping rules is met.

Unscheduled Interim Analysis will be performed if more than three patients have a DLT at the same dose level or if more than five patients in both tiers, at any dose level, have a DLT. In the former situation, further accrual to that dose level and higher dose levels will be suspended. In the latter situation, further accrual to the study will be halted. Reports of toxicity and efficacy will be submitted for DSMB review in that instance for review and guidance as to whether the dose level can be re-opened or accrual to the study can proceed and if the study should be amended to permanently close the problematic dose levels or closed altogether.

12.6 Reporting and Exclusions

12.6.1 Evaluation of Toxicity

All patients will be evaluable for toxicity from the time of their first treatment with vactosertib. Consultation with the Biostatistics Office will allow for completion of this section.

12.6.2 Evaluation of Response

All patients included in the study will be assessed for response to treatment if they have received at least 4 cycles of treatment. Consultation with the Biostatistics Office will allow for completion of this section.

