6.1 Schedule of Assessments

Table 1a. Tier 1 schedule of trial events 6.1.1

Tier 1 Schedule of Assessments	Screening	Treatment Tier 1															
		Cycle 1				Cycle 2				Cycle 3				Cycle 4			
Pre-study D-28 to -1		Wk1 ^a	Wk2 ^a	Wk3 ^a	Wk4 ^a	Wk5 ^a	Wk6 ^a	Wk7 ^a	Wk8 ^a	Wk9 ^a	Wk10 ^a	Wk11 ^a	Wk12 ^a	Wk13 ^a	Wk14 ^a	Wk15 ^a	Wk16 ^a
Informed Consent Form	X																
Inclusion/Exclusion Criteria	X															X	
Enrollment	X																
Demographics	X																
Diagnosis	X																
Medical History ^b	X	X	X	X	X	X	X	X	X	X	X	X	X	X	X	X	
Vital Signs	X	X	X	X	X	X	X	X	X	X	X	X	X	X	X	X	
Physical Examination ^c	X	X	X	X	X	X	X	X	X	X	X	X	X	X	X	X	
Medications	X	X	X	X	X	X	X	X	X	X	X	X	X	X	X	X	
ECOG	X	X	X	X	X	X	X	X	X	X	X	X	X	X	X	X	
Toxicity / AE assessment		X	X	X	X	X	X	X	X	X	X	X	X	X	X	X	
Con Med assessment		X	X	X	X	X	X	X	X	X	X	X	X	X	X	X	
Blood tests ^d	X	X	X	X	X	X	X	X	X	X	X	X	X	X	X	X	
Troponin, BNP, CK-MB	X													X			
EPO level	X					X				X				X			
Pregnancy test	X																
Electrocardiogram (EKG) ^e	X	e	e	e	e	e	e	e	e	e	e	e	e	e	e	e	

End of Tier 1 – Patients meeting composite response and toxicity endpoint may continue to accrue

Echocardiography with Doppler ^f	X																								
Bone Marrow Aspirate and Biopsy	X																								X
Ultrasound (left upper quadrant)	X																								X
Research blood	X	X						X								X					X			X	
Research Bone Marrow	X																								X
Treatment Administration Form and Compliance assessment		X	X	X	X	X	X	X	X	X	X	X	X	X	X	X	X	X	X	X	X	X	X	X	
MPN-SAF form		X	X	X	X	X	X	X	X	X	X	X	X	X	X	X	X	X	X	X	X	X	X	X	
Record HgB level and HgB change ^g		X	X	X	X	X	X	X	X	X	X	X	X	X	X	X	X	X	X	X	X	X	X	X	
Record RBC transfusion history		X ^h	X	X	X	X	X	X	X	X	X	X	X	X	X	X	X	X	X	X	X	X	X	X	
Composite response and toxicity endpoint assessment																									X

a. Visits are weekly if there is a dose change (escalated or reduced or held for toxicity). Visits are biweekly if dose is maintained. Visits are extended to every 4 weeks (once per cycle) as long as dose is maintained for 4 weeks.

b. Must record baseline comorbidities, pre-existing symptoms

c. Spleen size should be recorded

d. Blood tests are: CBC, CMP, UA, Phosphorous, LDH

e. Electrocardiogram required at screening. Only required at subsequent visits in the event of a dose increase.

f. Echocardiogram or Cardiac MRI will be done once every 2 cycles (8 weeks or 56 days)

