8.1.1 Discontinuation of Study Intervention

8.1.1. Tier 1 Stopping Rule:

The primary objective of Tier 1 is to assess the feasibility of protocol therapy in subjects with advanced MPNs as measured by the incidence of dose limiting toxicity (DLT, see *Definition of Dose Limiting Toxicity* section). Toxicities are assessed by CTCAEv5 criteria. Up to a total of 12 patients will be accrued to Tier 1. Tier 1 will be stopped for safety considerations under the following conditions:

- Any patient has grade 5 (lethal) DLT occurring within the first 12 weeks of starting vactosertib; or
- More than two patients experience a dose-limiting toxicity (DLT) at any dose, within the first 12 weeks on study.

Trial accrual will be suspended and a DSMB convened if either of these *Tier 1 Stopping Rule* criterion is triggered. If more than two patients have a DLT at the same dose level, then further accrual to that dose level and higher dose levels will be suspended. Pending review with DSMB, the study may be re-opened with amendment reflecting changes to the permitted dose levels. A planned stop to Tier 1 accrual will occur after 12 subjects have received at least one dose of vactosertib. At this time, the DSMB will be convened if fewer than 1 of the first 12 patients experience clinical benefit.

Protocol therapy will be considered safe if the *Tier 1 Stopping Rule* is not triggered. The following table provides the marginal probability of declaring the intervention unsafe for different rates of severe toxicity (as defined by *Tier 2 Stopping Rule*). This *Tier 1 Stopping Rule* protects against an unexpectedly high rate of severe toxicity.

Tier 1	True Rate of Severe Toxicity				
	5%	10%	15%	20%	30%
Probability of Declaring Unsafe	12%	35%	56%	73%	91%

If the Tier 1 safety boundaries are not crossed, this treatment strategy will be considered safe for expansion to Tier 2. Feasibility and toxicity will continue to be monitored in the Tier 2 portion of the study. A total of 37 patients will be accrued (Tier 1 + Tier 2) and the Tier 2 rule stopping rule applies to all subjects (up to 37) enrolled.

8.1.2. Tier 2 Stopping Rule:

- Any patient has grade 5 (lethal) DLT occurring within the first 12 weeks of starting vactosertib; or

- More than five patients experience a dose-limiting toxicity (DLT) at any dose, within the first 12 weeks on study.

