12.1 Study Design/Endpoints

12.1.1. Optimal Two-Stage Design, and Criteria to Proceed to Tier 2:

A Simon Two-stage Optimum Design was used to minimize the number of subjects exposed to vactosertib if it is found to be an unsuitable agent for the treatment of anemic patients with Ph-neg MPNs. Further development of vactosertib would be warranted if $\geq 20\%$ of subjects met *Criteria for Clinical Benefit* ([section 10.1](#)) without dose-limiting toxicity (see *Definition of Dose Limiting Toxicity* section). The study will be terminated early if fewer than 1 subject treated in the first tier (up to 12 subjects) meet these criteria. Using these criteria, there is less than a 10% chance of inappropriately accepting (α , type 1 error) vactosertib if it is not truly useful. Conversely, there is less than a 10% chance of inappropriately rejecting (β , type 2 error) vactosertib if it is actually a useful drug for anemic patients with Ph-neg MPNs.

Table 4: Optimal Two Stage Design

Response Probability Indicating Unacceptably Low vactosertib Activity	0.05
Response Probability Indicating Substantial vactosertib Activity	0.20
Probability of Accepting Poor Drug	0.1
Probability of Rejecting Good Drug	0.1
Number of Tier 1 Subjects	12
Number of Tier 1 Responders to Advance to Tier 2	≥ 1
Maximal Number of Subjects	37
Number of Tier 2 Responders to Advance Development	≥ 4

The Simon Two-stage Optimum Design is expected to minimize the number of subjects exposed to vactosertib if it is found to be an unsuitable agent for the treatment of anemic patients with Ph-neg MPNs (see *Criteria for Decision to Proceed to Tier 2* section). If 1 or more subjects meets the *Composite Response & Toxicity Endpoint* ([Table 5](#)) then the study will proceed to Tier 2 and another 25 subjects will be enrolled. After completion of Tier 2, if four or more subjects meet the *Composite Response & Toxicity Endpoint* then vactosertib

will have shown preliminary efficacy and feasibility to justify further evaluation as an agent to treat anemic patients with Ph-Neg MPNs.

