12.2.2 Composite response/ Toxicity measure

Responding subjects will have met *Criteria for Clinical Benefit* ([section 9.1](#)) for at least 8 weeks. This will ensure that a stable vactosertib dosing schedule can be achieved. Responding subjects will not experience dose limiting toxicity (see *Definition of Dose Limiting Toxicity*). Only subjects meeting all criteria will be considered responders.

Table 5: Composite Response & Toxicity Endpoint

Adequate Response	Meets Criteria for Clinical Benefit
Stable Response	Meets Criteria for Clinical Benefit to vactosertib for \geq 8 weeks
Tolerable	No Dose Limiting Toxicity Experienced

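### Section 12.6.2 assesses response only after at least 4 cycles, and the plan does not reconcile this with a two-stage rule on 12 and 37 treated patients or with Table 5, which needs 8 weeks of benefit

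*Combined protocol and SAP*

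**What the plan says.** Section 12.6.2 gives one rule for who is assessed: "All patients included in the study will be assessed for response to treatment if they have received at least 4 cycles of treatment". It then adds "Consultation with the Biostatistics Office will allow for completion of this section", so the rule is provisional by its own account.

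The decision rules count patients differently:

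- Section 12.1.1, on Tier 1: "The study will be terminated early if fewer than 1 subject treated in the first tier (up to 12 subjects) meet these criteria". Table 4 sets 12 patients in Tier 1, a maximum of 37, and cut-offs of at least 1 and at least 4 responders.
- Section 8.1.1, Tier 1 stopping rule: "A planned stop to Tier 1 accrual will occur after 12 subjects have received at least one dose of vactosertib".
- Section 12.2 gives the total as 37, made up of 12 and 25.
- Section 12.4.2 also sets its thresholds on full accrual: "If after complete accrual of 37 subjects, more than 11 patients meet criteria for Composite Response".

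Section 12.2.2 and Table 5 define the responder. Clinical benefit must have been met "for at least 8 weeks. This will ensure that a stable vactosertib dosing schedule can be achieved", and there must be no DLT. The section closes with "Only subjects meeting all criteria will be considered responders". No minimum number of cycles is given.

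**The concern.** A cycle is 4 weeks, so 12.6.2 requires 16 weeks of treatment, while Table 5 can be met after 8 weeks of benefit. Take a patient with benefit from week 4 to week 12 and no DLT who leaves at week 13. Under Table 5 this patient is a responder. Under 12.6.2 this patient is not assessed. Leaving before 4 cycles is foreseen (6.3.3.3.2, 7.9.2 and 8.2), so the case can arise.

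Two things are at stake, and they need different assumptions:

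1. If patients with fewer than 4 cycles are dropped from the denominator and are mostly failures, the reported response rate is too high.
2. If a patient who met Table 5 is not counted, a responder is lost to a rule that advances Tier 1 on a single one.

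**Working it through.** **Inputs.** From Table 4: 12 then 37 patients, unacceptable rate 0.05, target rate 0.20, continue with at least 1 responder, succeed with at least 4. From Table 5: 8 weeks of benefit. From 12.6.2: 4 cycles, that is 16 weeks. The documents give no rate of leaving before 16 weeks; call it d and assume 10-40%.

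**Step 1: reproduce the design.** P(go | p) = sum over x from 1 to 12 of Bin(x; 12, p) × P[Bin(25, p) ≥ 4 − x].

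- P(go | 0.05) = 0.0935, below the stated 0.10.
- P(go | 0.20) = 0.902, so the type 2 error is below the stated 0.10.
- P(0 of 12 | 0.20) = 0.80^12 = 0.0687.

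The plan's figures reproduce with denominators of exactly 12 and 37.

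**Step 2: early leavers dropped from the denominator.** Take a true rate of 15%, an illustrative value between the two design rates. If a share r of responders leaves early, the reported rate is 0.15(1 − r)/(1 − d).

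| d | all leavers are failures (r = 0) | responders leave at half the overall rate (r = d/2) | leaving unrelated to response (r = d) |
|---|---|---|---|
| 10% | 16.7% | 15.8% | 15% |
| 20% | 18.8% | 16.9% | 15% |
| 30% | 21.4% | 18.2% | 15% |
| 40% | 25.0% | 20.0% | 15% |

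The decisions use counts, so dropping failures does not move them. For example, 4 responders are 4/37 = 10.8% of all treated or 4/30 = 13.3% of 30 assessed, and both meet the cut-off of 4.

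**Step 3: Table 5 responders who leave before week 16 are not counted.** Assume that benefit starts at week b, uniform over weeks 0-8, so Table 5 is met at week b + 8 and the patient can still be lost for 8 − b weeks. Assume a constant weekly hazard h = −ln(1 − d)/16. The share of Table 5 responders lost is L = 1 − (1 − e^(−8h))/(8h).

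- d = 10%: 8h = 0.0527 and L = 2.6%. The counted rate is 0.20 × 0.974 = 0.195, and power is 0.892. P(0 of 12) = 0.0743, up 0.6 points.
- d = 20%: 8h = 0.1116 and L = 5.4%. The counted rate is 0.20 × 0.946 = 0.189, and power is 0.880. P(0 of 12) = 0.0807, up 1.2 points.

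If responders leave at half that hazard, power is 0.897 and 0.892. If onset in the 24-week Tier 2 is spread over weeks 0-16 instead, the Tier 2 loss halves to 1.3% and 2.7%, and power is 0.894 and 0.884.

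**The case against.** **Most early leavers are already classified.** A reader might infer that the plan says nothing about a patient with fewer than 4 cycles. That is too strong. Section 12.2.2 alone makes anyone with a DLT, or with less than 8 weeks of benefit, a non-responder. What remains open is the patient who met Table 5 and then left, and whether the others stay in the denominator.

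**Four cycles may be a time point, not an exclusion.** In the Tier 1 schedule the row "Composite response and toxicity endpoint assessment" is marked at the end of the tier, the work-up in 6.3.5 falls at the end of Cycle 4, and 10.1 uses the criteria to decide on treatment beyond 4 cycles. Six cycles in Tier 2 also satisfy a floor of four. This reading is fair and may be what was meant. But 12.6.2 stands under the heading on reporting and exclusions and is worded as a condition on the patient. Even as a time point, it does not say how someone who left earlier with Table 5 met is counted.

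**Type 1 error.** A reader might infer that early leavers will be replaced until 12 and 37 are assessable, which could push the error above 0.10. No passage provides for replacement, and 8.1.1 closes Tier 1 accrual on patients dosed.

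**Power.** A reader might also infer a large loss by applying the whole early-loss rate to responders. A patient who leaves before completing 8 weeks of benefit fails Table 5 whatever 12.6.2 says. Only the gap between meeting Table 5 and week 16 is due to 12.6.2, and that gap is short.

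**Conclusion.** The concern holds and should be fixed, but its numerical effect is modest. Section 12.6.2 is an unfinished rule that, read literally, disagrees with the treated-patient counts in 12.1.1, 8.1.1 and 12.2 and with the responder definition in 12.2.2.

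The effect on the reported rate runs from none (leaving unrelated to response) to 15% reported as 17-25% (all leavers fail, 10-40% early loss). It changes neither go/no-go decision. The effect on power is about 1-2 points at 10-20% early loss, with 0.6-1.2 points of added Tier 1 stopping at a true 20% rate. All of these sizes rest on an assumed early-loss rate; the power figures also rest on the assumed onset window and constant hazard. The inconsistency itself needs no assumption.

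**What to change.** Replace the rule in 12.6.2 with wording such as:

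> The response set is all patients who received at least one dose, each counted once and not replaced. A patient who met Table 5 before leaving is a responder whatever the number of cycles; any other patient who leaves early is a non-responder.

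Report the set with at least 4 cycles, with its denominator, as a sensitivity analysis only. Remove the placeholder sentence once the text is settled.

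The cost is protocol wording, with no added visits. The design keeps its 12 and 37 patients and its error rates. Two consequences should be accepted openly. The reported rate may be lower than under the 4-cycle rule. For early leavers, response will rest on what follow-up visits record under 6.3.2 (hemoglobin, transfusions, symptoms and palpated spleen), because spleen ultrasound is scheduled only at screening and end of tier. The imaging criterion in 10.1.2 may therefore be unavailable for them.
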